7.4 Long-Term Follow-up | Re-contacting Subjects

Follow-up occurs three months post-intervention for final data collection. Otherwise, there is no further follow up that takes place.

8.0 DATA HANDLING AND RECORD KEEPING

8.1 Data Collection

We will retain de-identified screening data (which includes the initial 11 eligibility questions as well as the remaining demographic questions) so that we can determine who among those screened were ineligible for participation and why. To help protect a person's identification, we will omit the day of someone's birthday (MM/DD/YYYY) from the record for anyone who is screened but does not participate in the study. This will be informative to future studies about general interest in studies of this kind and screening criteria that might need to be changed.

Potential participants will also be asked whether or not they would like to be contacted for future studies. Individuals who agree to this will provide their contact information to be recontacted over the phone or in person. The study team will store their contact information for future study eligibility. Contact for future studies would include other future studies not yet planned or funded. Retaining these data will be helpful for future study recruitment.

Preliminary screen data regarding eligibility criteria will be stored in a locked file cabinet in a locked room at the School of Social Work. Only approved study personnel have access to the files.

Individuals who agree to be contacted in the future will have their contact information stored in a secure, password -protected file with only their name and contact information.

Participants who do not enroll in the study and do not wish to be recontacted for future studies will have their contact information destroyed.

8.2 Confidentiality and Privacy

Data collection conducted with fathers, caregivers, and children will generally be done on an individual basis (either alone or the father (or caregiver) and child together as appropriate). In most cases, survey completion will be done virtually. This will ideally be conducted through a virtual video-call in which research team members can share their computer screen with data collection instruments pulled up to walk the participant through the documents together. In other cases, this may be done through a phone call where the researcher reads prompts to the participants to answer. In as few cases as possible and as a last case scenario, survey completion may be completed in participant's homes, in private rooms located at local libraries, or in office space provided by partner community agencies through safe and socially distanced protocols. In all cases, the utmost precaution will be taken to ensure that other individuals are not in the vicinity and cannot overhear the researcher asking, or the participant answering questions.

If someone else is in the location, we will continue with the interview only if other individuals are at a sufficient distance so as to be unable to hear the questions and responses. In no situation would an interview be continued or conducted if the privacy of the respondent would be compromised by the specific circumstances of the interview.

8.3 Records Retention

The few questions audio recorded in the interviews will be digitally recorded and transcribed by the study team. Once the transcription has been verified by the PI, the audio file will be deleted. The use of audio recordings is important to allow for the interviewer to focus on the questions with the participants without having to take detailed notes that could yield less accurate data.

Transcripts will be stored on campus resources for at least 7 years after the project ends per the research records retention policy.

Subjects will be notified in the consent form about the use of photos. The PI also has a photo release form that could be used in addition to obtaining permission to use photos of participants when disseminating findings. Photos, like the audio data, will be retained for at least 7 years after the project ends.

8.4 Protocol Deviations

A protocol deviation is any noncompliance with the clinical trial protocol or investigational plan requirements. The noncompliance may be either on the part of the subject, the investigator, or the study site staff. As a result of deviations, corrective actions are to be developed by the site and implemented promptly.

It is the responsibility of the Principal Investigator/site investigator/study staff to use continuous vigilance to identify and report deviations. The Principal Investigator is responsible for assessing whether the deviation constitutes noncompliance as defined by the reviewing IRB and if so, reporting it within the required time frame(s). The site investigator is responsible for knowing and adhering to the reviewing IRB requirements.

8.5 Publication and Data Sharing Policies

This study will be conducted in accordance with the following publication and data sharing policies and regulations:

National Institutes of Health (NIH) Public Access Policy, which ensures that the public has access to the published results of NIH funded research. It requires scientists to submit final peer-reviewed journal manuscripts that arise from NIH funds to the digital archive PubMed Central (<https://www.ncbi.nlm.nih.gov/pmc/>) upon acceptance for publication.

This study will comply with the NIH Data Sharing Policy and Policy on the Dissemination of NIH-Funded Clinical Trial Information and the Clinical Trials Registration and Results Information Submission rule. As such, this trial will be registered at ClinicalTrials.gov, and results information from this trial will be submitted to ClinicalTrials.gov. In addition, every attempt will be made to publish results in peer-reviewed journals. Data from this study may be requested from other researchers 5 years after the completion of the primary endpoint by contacting the PI, [name], *[contact]*.

9.0 STUDY ANALYSIS

9.1 Statistical Hypotheses

- Primary Efficacy Endpoint(s):**

For feasibility and acceptability measures, we are not testing hypotheses. We are examining elements of the intervention to assess client acceptance of the treatment, ability to recruit sufficient numbers of participants, and feasibility of delivery with the clients and therapists in the treatment settings.

- Secondary Efficacy Endpoint(s):**

We hypothesize that participants who are in the intervention will have improved relationship, parenting, parent-child, and mental health outcomes after completing the intervention. Alternatively, our null hypothesis is that there will be no difference in the effects of the intervention for relationship, parent-child, parenting, and mental health outcomes.

9.2 Sample Size Justification

The sample size for this feasibility pilot study is based on previous research and not to formally test hypotheses. Its purpose is largely to develop an intervention, identify measures, and assess logistical nature of the proposed intervention. The secondary outcomes, while they can be tested in pre- and post-test analyses, are included to determine trends or patterns of responses.

9.3 Subject Population(s) for Analysis

Participants who completed the full intervention and the pre- and post-test interview (including both father and caregiver participants) will be included in the analyses.

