In addition to the classroom component that PIO provides, the program will offer a therapeutic component. These sessions will also be done virtually. Weekly, those receiving services from Pathways for Parents after Incarceration will be invited to take part in a remote peer support group-style group session led by a provider within the community, Anesis Family Therapy. This component of the program is rooted in systems therapy and uses narrative therapy, trauma focused cognitive therapy, and motivational interviewing techniques. This aspect promotes fathers' and caregivers' ability to identify their values and skills so they can effectively confront the challenges (both instrumental and relational) that they face during their reentry period and as family members working to support the fathers. These sessions will run for 45-60 minutes following the classroom portion (PIO).

The program (both classroom and therapeutic peer support) will be offered weekly in virtual, remote format on for 8 continuous weeks (the 9th week will be a class graduation/celebration). Any participant that does not have access to a computer will be loaned laptops or tablets and internet hotspots. The structure of the sessions are as follows:

5:00pm - virtual classroom opens and PIO course activities begin
7:00pm - PIO class concludes and 30 minute break begins
7:30pm - therapeutic peer support
8:30pm - wrap up

These sessions will provide gift card or cash incentives for attending and completing class material. Food will be delivered to their home in lieu of providing food in person during group meetings as was originally planned before COVID-19.

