6.0 BEHAVIORAL/SOCIAL INTERVENTION

6.1 Study Behavioral or Social Intervention Description

The Pathways for Parents after Incarceration Program (P4P) is an 8-week intervention that focuses on strengthening parenting skills, building constructive co-parenting strategies, providing therapeutic social support, and connecting families to needed specialized services. P4P is based on an adapted version of Parenting Inside Out (PIO), a cognitive behavioral parent management skills training program originally designed for parents in prison.

P4P is delivered remotely over Zoom (owing to the COVID-19 pandemic) but in real time. Participants first pick up materials needed for the intervention (e.g., intervention manual, laptop/tablet, office supplies, other materials), and then participate from home or other location of their choice. Eight didactic sessions (once per week for eight weeks) are completed along with eight therapeutic sessions (these run back-to-back). Trained PIO coaches deliver the didactic classroom portion and trained therapeutic clinicians deliver the therapeutic sessions. The PIO or classroom portion lasts 2-2.5 hours each, and the therapeutic session is 1 hour each week (total time = 3-3.5 hrs/week).

Staff who will administer the intervention must first complete a PIO training offered by the organization who owns the curriculum rights to the intervention, The Pathfinder Network (<https://www.thepathfindernetwork.org/>). Clinical staff who facilitate the therapeutic sessions must be trained and licensed clinicians in social work, counseling, psychology or related fields. Intervention fidelity will be monitored using the Parenting Inside Out Group Observation Feedback Form Score. Domains scoring in the low category (1=remediation is needed or 2=a growth area) will signal inadequate fidelity requiring re-training and further monitoring. This will be done through individual meetings with the interventionist and with written feedback.

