6.2 Study Intervention Compliance

Adherence to the protocol will be assessed by documenting the number of participants recruited, consented and enrolled, and attendance of participants in weekly PIO and therapeutic sessions. Completion of study interviews (measures and qualitative interviews) will also be tracked. To remain an active participant in the study, participants must attend all PIO sessions and if any are missed, attend a makeup session with a coach. Attendance records are carefully monitored and tracked. Participants who drop out of the study once the sessions begin will not be replaced.

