9.4 Statistical Methods

Primary outcomes will be assessed using descriptive statistics. Specifically, count data (e.g., number of enrolled participants who complete the intervention) are presented using percentages. Continuous measures presented as a score on a scale (e.g., provider adherence scores) are presented with means and standard deviations, and minimum and maximum scores.

Secondary outcomes will be assessed using paired sample t-tests to estimate changes between the scales at baseline and post-test. Two-tailed tests with .05 p-values will be used.

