9.5 Handling of Missing Data

Complete-case analysis will be used and participants with missing data (i.e., missing post-test interview) will be excluded from the analysis.

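### Section 9.3 restricts the analyses to programme completers without confining this to the pre/post tests, which conflicts with the 9.4 completion example and adds a selection that 9.5 does not state

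*Combined protocol and SAP*

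**What the plan says.** Section 9.3 states one population: "Participants who completed the full intervention and the pre- and post-test interview (including both father and caregiver participants) will be included in the analyses". It sits under a heading that covers both the primary feasibility and acceptability measures and the secondary pre/post outcomes, and it does not say which it governs.

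Two neighbouring sections bear on it:

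- Section 9.4, on primary outcomes: "count data (e.g., number of enrolled participants who complete the intervention) are presented using percentages". This implies an enrolled denominator for completion.
- Section 9.5, also without naming an endpoint: "participants with missing data (i.e., missing post-test interview) will be excluded from the analysis". It mentions the missing interview, not programme completion.

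The plan does not define what finishing the whole programme means. Section 6.1 says "Eight didactic sessions (once per week for eight weeks) are completed along with eight therapeutic sessions". Section 2.2 says participants "will be invited to take part in a remote peer support group-style group session", and it describes family activities as a third component. Section 6.2 sets a rule for staying active, that "participants must attend all PIO sessions and if any are missed, attend a makeup session with a coach", but does not call this completion and sets no threshold for the therapeutic sessions.

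The raw data are collected in any case. Section 6.2 provides for "documenting the number of participants recruited, consented and enrolled, and attendance of participants in weekly PIO and therapeutic sessions" and tracks completion of interviews, section 7.1 defines enrolment, and section 7.4 adds a later wave: "Follow-up occurs three months post-intervention for final data collection".

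**The concern.** Acceptance by participants, with retention as the named example, is the first aim of the pilot, and section 4.1 says the pilot is to identify what a later randomised trial needs. Retention and attendance are among the figures that trial would plan from. As written, two analysts could choose different denominators for them and each could cite the plan. A post-test retention figure computed among people selected for having a post-test tells the reader nothing. Attendance, satisfaction and three-month retention among completers leave out the people whose experience bears most on acceptability.

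The pre/post comparison has a separate problem. A paired test needs both interviews, and that is not in dispute. Filtering on programme completion as well selects participants on something that happens after baseline and may be related to how much they change.

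**Working it through.** **The plan's own figure.** The synopsis gives a headcount only: 15 + 15 + 15 = 45 and 15 + 15 + 20 = 50, and the listed total of 47 lies in that range. There is no completion, retention or dropout figure to reproduce. Below, 15 fathers is the planned number and every other count is an assumption. No caregiver figure is given, because section 5.3 lets a father enrol when the caregiver declines or does not reply, so the number of caregivers is not assured.

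**1. Which set applies to which measure**

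| Measure | Set given outside 9.3 | If 9.3 is applied |
|---|---|---|
| Recruitment counts, provider adherence scores | not based on a participant completer set | unaffected |
| Completion | enrolled (9.4 example) | conflict with 9.4 |
| Post-test retention | none | 100% for any number of completers |
| Three-month retention, attendance, satisfaction | none | completers only |
| Paired t-tests | post-test required (9.5) | post-test and programme completion required |

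**2. Retention and attendance.** Let c fathers complete and give both interviews. Assume that no non-completer gives a later interview, 2 completers are lost by three months, completion follows the 6.2 rule with makeups counted, and each non-completer attends 3 of 8 PIO sessions.

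- Post-test retention: c/15 of enrolled, c/c of the 9.3 set.
- Three-month retention: (c − 2)/15 of enrolled, (c − 2)/c of the 9.3 set.
- PIO attendance: [8c + 3(15 − c)]/120 over enrolled, 8c/8c in the 9.3 set.

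| c | Post-test: enrolled vs 9.3 | Three-month: enrolled vs 9.3 | PIO attendance: enrolled vs 9.3 |
|---|---|---|---|
| 9 | 60.0% vs 100% | 7/15 = 46.7% vs 7/9 = 77.8% | 90/120 = 75.0% vs 100% |
| 12 | 80.0% vs 100% | 10/15 = 66.7% vs 10/12 = 83.3% | 105/120 = 87.5% vs 100% |
| 14 | 93.3% vs 100% | 12/15 = 80.0% vs 12/14 = 85.7% | 115/120 = 95.8% vs 100% |
| 15 | 100% vs 100% | 13/15 = 86.7% for both | 120/120 = 100% for both |

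**3. Satisfaction.** If 10 of 15 complete and 9 of those 10 are satisfied, the completer figure is 9/10 = 90.0%. Over all enrolled it lies between 9/15 = 60.0% (no non-completer satisfied) and 14/15 = 93.3% (all 5 satisfied).

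**4. Paired tests.** Suppose k non-completers give both interviews alongside 12 completers. If the non-completers' mean change is zero, the mean change is 12/(12 + k) of the completer value: 100%, 92.3%, 85.7% and 80.0% for k = 0, 1, 2, 3. If they change half as much, it is (12 + 0.5k)/(12 + k): 100%, 96.2%, 92.9% and 90.0%.

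**5. The completion count itself.** Even with the enrolled denominator, the numerator is open. If 12 of 15 finish PIO and 0, 2 or 4 of them miss a therapeutic session, completion is 12/15 = 80.0%, 10/15 = 66.7% or 8/15 = 53.3% when therapeutic sessions count, and 80.0% throughout when they do not. The family activities could move it further.

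**The case against.** The best defence is that 9.3 was meant for the secondary outcomes only. Section 9.2, just before it, speaks of testing those outcomes before and after the programme. Section 9.3 then asks for both interviews, and 9.4 applies paired tests to the secondary outcomes alone. Recruitment counts and adherence scores need no interview pair. This reading is plausible and may be the intended one. But 9.3 does not say it, and adopting it would still leave retention, attendance and satisfaction without a denominator.

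A reader might infer something stronger: that the plan will report completion and retention of 100% by construction. The documents do not support that. The 9.4 example counts completers among the enrolled, section 6.2 tracks enrolled numbers and attendance, and three-month retention would not be fixed at 100% even in the 9.3 set. Nor do 9.3 and 9.5 contradict each other, since they can be applied together.

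On the paired tests, a completer set fits the 9.1 hypothesis, which is worded for outcomes once the programme has been completed, and 9.2 presents these outcomes as trends. Sections 6.2 and 7.3 also suggest that few people who miss PIO sessions will give a post-test. So a completer analysis is defensible if labelled as such. What remains is that it is the only set planned. Someone who attended every PIO session, missed therapeutic sessions and gave both interviews could be dropped, depending on how completion is read.

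It is also fair that section 9 names no three-month endpoint and that every size shown is assumed.

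**Conclusion.** The concern holds as an unresolved conflict between 9.3 and 9.4, together with a completer filter on the paired tests that 9.5 does not state. It does not show that the completion percentage will be wrong, because 9.4 suggests an enrolled denominator for that count.

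The size cannot be fixed from the documents. Under the stated assumptions, with 9 to 15 of 15 fathers completing, the choice of set moves post-test retention by 40 to 0 percentage points and three-month retention by 31 to 0. With up to 3 non-completers added to 12 completers, the mean pre/post change is 80% to 100% of the completer value. The denominator issue disappears if everyone enrolled completes and gives both interviews. The paired-test issue disappears if everyone completes or no non-completer gives a post-test.

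The missing definition of completion is a supporting point. Overall this is a cheap and worthwhile improvement, because it touches the pilot's first aim.

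**What to change.** 1. State in 9.3 that it applies to the secondary pre/post tests only. Report completion, session attendance, interview completion and retention (post-test and three-month) over all enrolled participants as defined in 7.1, by role, using the actual number enrolled in each role. Show the number who started sessions as well, because enrolment under 7.1 does not require starting and pre-session withdrawals should be visible separately. Report satisfaction as respondents out of enrolled.
2. For the paired t-tests, include all enrolled participants with both interviews, whether or not they finished the programme. Keep the completer set as a labelled sensitivity analysis that preserves the 9.1 wording. Name the same main set in 9.3 and 9.5.
3. As a supporting clarification, say how PIO sessions, makeups, therapeutic sessions and the family activities in 2.2 count toward completion, and use that definition for the 9.4 percentage.

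The cost is wording only, since section 6.2 already tracks enrolment, attendance and interview completion. The downsides are less favourable retention and attendance figures, possibly smaller pre/post changes, and a main pre/post set that departs from the 9.1 phrasing. The change does not recover satisfaction ratings from people who leave: section 3.0 places that measure after the intervention, and the withdrawal visit in 7.3 does not list it.

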9.4 Statistical Methods

Primary outcomes will be assessed using descriptive statistics. Specifically, count data (e.g., number of enrolled participants who complete the intervention) are presented using percentages. Continuous measures presented as a score on a scale (e.g., provider adherence scores) are presented with means and standard deviations, and minimum and maximum scores.

Secondary outcomes will be assessed using paired sample t-tests to estimate changes between the scales at baseline and post-test. Two-tailed tests with .05 p-values will be used.

9.5 Handling of Missing Data

Complete-case analysis will be used and participants with missing data (i.e., missing post-test interview) will be excluded from the analysis.

10.0 RISK/BENEFIT ASSESSMENT

10.1 Known Potential Benefits

There are no direct benefits to subjects. However, there are potential benefits to participants which include the parenting strategies that the fathers will learn in the community-based program.

The potential benefits for society derive from the scientific advances that may occur as a result of this study through intervention development and future efficacy and effectiveness trials. There is the possibility of public benefit because of the potential to positively influence previously incarcerated parents and their children. Additionally, information learned in the study may be used to inform the research and social welfare policy community to improve services provided to incarcerated parents that could prevent or reduce further criminal justice involvement and criminal behavior post-prison.

